3.5.2.4 Pregnancies

Any pregnancy that occurs during study participation should be reported using a Clinical Trial Pregnancy Form. To ensure patient safety each pregnancy must also be reported to IQVIA within 24 hours of learning of its occurrence. IQVIA on its turn will promptly inform Recordati. The pregnancy should be followed up to determine outcome, including spontaneous or voluntary termination, details of birth, and the presence or absence of any birth defects or congenital abnormalities or maternal and newborn complications. Instructions about completing initial and follow-up Clinical Trial Pregnancy Forms and sending them to IQVIA are given in [Section 7.1.2](#).

3.5.2.5 QT prolongation

Pasireotide s.c. has been shown to prolong the QT interval on the ECG in two dedicated healthy volunteer studies. The clinical significance of this prolongation is unknown.

In clinical studies in Cushing's disease patients, QTcF of >500 msec was observed in two out of 201 patients. These episodes were sporadic and of single occurrence with no clinical consequence observed. Episodes of torsade de pointes were not observed either in those studies or in clinical studies in other patient populations.

Pasireotide s.c. should be used with caution and the benefit risk ratio carefully weighed in patients who are at significant risk of developing prolongation of QT, such as those:

- with congenital long QT syndrome.

- with uncontrolled or significant cardiac disease, including recent myocardial infarction, congestive heart failure, unstable angina or clinically significant bradycardia.
- taking antiarrhythmic medicinal products or other substances that are known to lead to QT prolongation.
- with hypokalemia and/or hypomagnesaemia.

Monitoring for an effect on the QTc interval is advisable and ECG is recommended prior to the start of pasireotide s.c. therapy, one week after the beginning of the treatment and as clinically indicated thereafter. Hypokalaemia and/or hypomagnesaemia must be corrected prior to administration of pasireotide s.c. and should be monitored periodically during therapy.

QTcF/QTcB prolongations > 480 msec will be reported as adverse events in this study.

3.5.2.6 Glucose metabolism

Alterations in blood glucose levels have been frequently reported in healthy volunteers and patients treated with pasireotide. Hyperglycaemia and, less frequently, hypoglycaemia, were observed in subjects participating in clinical studies with pasireotide s.c.

The degree of hyperglycaemia appeared to be higher in patients with pre-diabetic conditions or established diabetes mellitus. During the pivotal study, HbA1c levels increased significantly and stabilized but did not return to the baseline values. Less cases of discontinuation and lower reporting rate of severe AEs due to hyperglycaemia have been reported in patients treated with the dose of $600\mu\text{g}$ b.i.d.

The development of hyperglycaemia appears to be related to decreases in secretion of insulin (particularly in the post-dose period) and of incretin hormones (i.e. glucagon-like peptide-1 [GLP-1] and glucose-dependent insulinotropic polypeptide [GIP]).

Glycaemic status (fasting plasma glucose/haemoglobin A_{1c} [FPG/HbA_{1c}]) should be assessed prior to starting treatment with pasireotide s.c. FPG/HbA_{1c} monitoring during treatment should follow established guidelines. In addition, monitoring of FPG 4 weeks and HbA_{1c} 3 months after the end of the treatment is recommended. Self-monitoring of blood glucose and/or FPG assessments should be done every week for the first two to three months and periodically thereafter, as clinically appropriate.

If hyperglycemia develops in a patient being treated with pasireotide s.c., the initiation or adjustment of antidiabetic treatment is recommended, following the established treatment guidelines for the management of hyperglycemia. In the majority of patients who developed hyperglycaemia, the condition appeared to be manageable with appropriate antidiabetic therapy. If uncontrolled hyperglycaemia persists despite appropriate medical management, the dose of pasireotide s.c. should be reduced or pasireotide s.c. treatment discontinued.

Cushing's disease patients with poor glycaemic control (as defined by HbA_{1c} values $>8\%$ while receiving antidiabetic therapy) may be at higher risk of developing severe hyperglycaemia and associated complications. In patients with poor glycemic control the diabetes management should be intensified prior to initiation and during pasireotide therapy.

3.5.2.7 Cardiac disease

Bradycardia has been reported with the use of pasireotide s.c. Careful monitoring is recommended in patients with cardiac disease and/or risk factors for bradycardia, such as history of clinically significant bradycardia or acute myocardial infarction, high-grade heart block, congestive heart failure (NYHA Class III or IV), unstable angina, sustained ventricular tachycardia, ventricular fibrillation. Dose adjustment of medicinal products such as beta blockers, calcium channel blockers, or medicinal products to control electrolyte balance, may be necessary.

3.5.2.8 Laboratory evaluations

Mild transient elevations in aminotransferases are observed commonly in patients treated with pasireotide. Rare cases of concurrent elevations in ALT greater than 3xULN and bilirubin greater than 2xULN have also been observed.

Monitoring of liver function is recommended prior to treatment with pasireotide s.c. and after one, two, four, eight and twelve weeks during treatment. Thereafter liver function should be monitored as clinically indicated.

Patients who develop increased transaminase levels should be monitored with a second liver function evaluation to confirm the finding. If the finding is confirmed, the patient should be followed with frequent liver function monitoring until values return to pre-treatment levels. Therapy with pasireotide s.c. should be discontinued in case the patient develops jaundice or other signs suggestive of clinically significant liver dysfunction, in case of a sustained increase in AST or ALT of 5x ULN or greater, or if ALT elevations greater than 3xULN occur concurrently with bilirubin elevations greater than 2xULN. Following discontinuation of treatment with pasireotide s.c. patients should be monitored until resolution.

As the pharmacological activity of pasireotide s.c. mimics that of somatostatin, inhibition of pituitary hormones other than ACTH cannot be ruled out. Monitoring of pituitary function (e.g. TSH/free T₄, GH/IGF-1) before and periodically during pasireotide s.c. therapy should therefore be considered, as clinically appropriate.

Available data on the following laboratory parameters will be collected in this study:

- AST
- ALT
- Alkaline phosphatase
- γ GT
- α -amylase
- Total bilirubin
- WBC
- RBC
- Hemoglobin
- Hematocrit
- Platelets
- Sodium

- Potassium
- Magnesium
- Fasting Plasma Glucose
- HbA1C
- GH
- IGF-1
- TSH
- Free T4
- PT
- APTT

If total bilirubin concentration is increased above 2.0 times upper limit normal (ULN), total bilirubin is recommended to be differentiated into the direct and indirect reacting bilirubin.

All local laboratories contributing to the study should provide the sponsor with a copy of each laboratory's certification and a tabulation of the normal ranges and standard deviations from control values for each of the parameters being evaluated. These laboratory references should be forwarded to the sponsor prior to study start and updated promptly if any information changes during the course of the study.

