6.5.2 Safety evaluation

For all safety analyses, the safety set will be used. Safety analysis will be stratified by incident or prevalent use of the drug.

Safety and tolerability assessments include AEs, vital signs, blood pressure, heart rate, body temperature, blood glucose (fasting plasma glucose, HemoglobinA1c), hormones (GH, IGF-1, TSH/free T₄), liver enzymes (AST, ALT, alkaline phosphatase, γGT, total bilirubin), hematology, electrolytes, immunological events (e.g., allergic reactions: rash, pruritus, injection site reactions), gallbladder ultrasound and ECGs.

The overall safety observation period will be divided into two mutually exclusive segments:

1. on-treatment period: from day of enrolling into the study to 28 days after last dose of pasireotide s.c.-
2. post-treatment period: starting at day 28+1 after last dose of pasireotide s.c.

Safety data will be largely collected for the on-treatment period.

For continuous safety variables, the change from the last dose of pasireotide s.c. to 3 months after permanent discontinuation of pasireotide s.c. for patients that discontinue pasireotide s.c. prior to completing the 3-year observation period will be summarized.

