6.5.2.2 Laboratory evaluations

All laboratory values will be converted into SI units.

The frequency of laboratory abnormalities will be summarized for each parameter. Laboratory data will also be summarized via shift tables. A listing of laboratory values will be provided by laboratory parameter, patient and visit window. No imputation for missing values will be done for laboratory variables and they will be identified as missing.

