#### **8.4.2 Laboratory evaluation**

All laboratory values will be converted into SI units.

Laboratory data will be classified (by biostatistics/SAS programming) into CTC grades according to the NCI Common Terminology Criteria for Adverse Events (CTCAE) v3.0. A severity grade of 0 will be assigned when the value is within normal limits. In the unlikely case when a local laboratory normal range overlaps into the higher (i.e. non-zero) CTC grade, the laboratory value will still be taken as within normal limits and assigned a CTC grade of zero.

For some laboratory tests, CTC grades are defined in two directions (low and high, e.g. for potassium: hypokalemia and hyperkalemia). The two directions will be analyzed separately.

The following summaries will be produced for the laboratory data (by laboratory parameter and direction of abnormality, as applicable):

- Shift tables using CTC grades to compare baseline to the worst post-baseline value
- Shift tables using CTC grades to compare the last post-baseline grade on treatment to the worst grade during the 90 days after permanent discontinuation of pasireotide s.c., in patients who discontinued pasireotide s.c. prematurely.
- For laboratory parameters where CTC grades are not defined, shift tables to the minimum and maximum post-baseline value using the low/normal/high classifications based on laboratory reference ranges.

Patients with laboratory values outside the laboratory reference range will be listed and flagged to show the corresponding CTC grades and the classifications relative to the laboratory reference ranges. In addition, laboratory values of patients with laboratory abnormalities of CTC grade 3 or 4 will be presented in separate listings.

HbA1c values will be classified into categories <5.7%, >=5.7% - <6.5% >=6.5% - 8% and >=8%, and categories cross-tabulated in shift tables (baseline versus worst post-baseline category).

---

Study Code: CSOM230B2410

A similar analysis will be performed for fasting glucose, classified into categories <100 mg/dL, >=100-<126 mg/dL, >=126 mg/dL (baseline versus worst post-baseline category).

The analyses of glucose will only include patients who were fasting at the time of blood sampling.

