## 9.2 AESI LIST

Category	Adverse Event Term
AESI Bradycardia related AEs	Atrial conduction time prolongation (PT) Atrioventricular block (PT) Atrioventricular block complete (PT) Atrioventricular block second degree (PT) Atrioventricular dissociation (PT) Bradycardia (PT) Central bradycardia (PT) Conduction disorder (PT) Defect conduction intraventricular (PT) Electrocardiogram PQ interval prolonged (PT) Electrocardiogram PR prolongation (PT) Electrocardiogram QRS complex prolonged (PT) Electrocardiogram QT prolonged (PT) Long QT syndrome (PT) Paroxysmal atrioventricular block (PT) Sinoatrial block (PT) Sinus bradycardia (PT)
AESI Coagulation related AEs	Blood fibrinogen decreased (PT) Blood thrombin decreased (PT) Blood thromboplastin abnormal (PT) Blood thromboplastin decreased (PT) Coagulation factor IX level decreased (PT) Coagulation factor V level decreased (PT) Coagulation factor VII level decreased (PT) Coagulation factor X level decreased (PT) Coagulation factor decreased (PT) Hypofibrinogenaemia (PT) International normalised ratio abnormal (PT) Prothrombin level decreased (PT) Prothrombin time prolonged (PT) Prothrombin time ratio decreased (PT) Thrombin time prolonged (PT)
AESI Gallbladder and biliary related AEs	Bile duct necrosis (PT) Bile duct obstruction (PT) Bile duct stenosis (PT) Bile duct stone (PT) Bile output abnormal (PT) Bile output decreased (PT)

Study Code: CSOM230B2410

Category	Adverse Event Term
	Bile output increased (PT)
	Biliary cirrhosis (PT)
	Biliary colic (PT)
	Biliary dilatation (PT)
	Biliary dyskinesia (PT)
	Biliary dyspepsia (PT)
	Biliary fibrosis (PT)
	Biliary fistula (PT)
	Biliary ischaemia (PT)
	Biliary tract disorder (PT)
	Bilirubin conjugated abnormal (PT)
	Bilirubin conjugated increased (PT)
	Bilirubin excretion disorder (PT)
	Bilirubin urine present (PT)
	Bilirubinuria (PT)
	Blood alkaline phosphatase abnormal (PT)
	Blood alkaline phosphatase increased (PT)
	Blood bilirubin abnormal (PT)
	Blood bilirubin increased (PT)
	Blood bilirubin unconjugated increased (PT)
	Cholangiogram abnormal (PT)
	Cholecystectomy (PT)
	Cholecystitis (PT)
	Cholecystitis acute (PT)
	Cholecystitis chronic (PT)
	Cholecystogram intravenous abnormal (PT)
	Cholecystogram oral abnormal (PT)
	Cholelithiasis (PT)
	Cholelithiasis migration (PT)
	Cholelithiasis obstructive (PT)
	Cholestasis (PT)
	Deficiency of bile secretion (PT)
	Endoscopy biliary tract abnormal (PT)
	Gallbladder disorder (PT)
	Gallbladder enlargement (PT)

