	Mean arterial pressure decreased (PT)
AESI Hypothyroidism related AEs	Blood thyroid stimulating hormone decreased (PT)
	Hypothyroidism (PT)
	Myxoedema (PT)
	Myxoedema coma (PT)
	Secondary hypothyroidism (PT)
	Thyroid dermatopathy (PT)
	Thyroid stimulating hormone deficiency (PT)
	Thyroxine free decreased (PT)
	Tri-iodothyronine decreased (PT)

Study Code: CSOM230B2410

Category	Adverse Event Term
	Tri-iodothyronine free decreased (PT)
AESI Injection site reaction related AEs	Administration site abscess (PT) Immediate post-injection reaction (PT) Injection site atrophy (PT) Injection site bruising (PT) Injection site discolouration (PT) Injection site discomfort (PT) Injection site erosion (PT) Injection site erythema (PT) Injection site exfoliation (PT) Injection site granuloma (PT) Injection site haematoma (PT) Injection site haemorrhage (PT) Injection site hypersensitivity (PT) Injection site inflammation (PT) Injection site irritation (PT) Injection site necrosis (PT) Injection site nodule (PT) Injection site oedema (PT) Injection site pain (PT) Injection site pruritus (PT) Injection site rash (PT) Injection site reaction (PT) Injection site swelling (PT) Injection site urticaria (PT)
AESI Liver safety related AEs	Alanine aminotransferase abnormal (PT) Alanine aminotransferase increased (PT) Ammonia increased (PT) Aspartate aminotransferase abnormal (PT) Aspartate aminotransferase increased (PT) Blood cholinesterase abnormal (PT) Blood cholinesterase decreased (PT) Computerised tomogram liver abnormal (PT) Gamma-glutamyltransferase abnormal (PT) Gamma-glutamyltransferase increased (PT) Guanase increased (PT) Hepatic enzyme abnormal (PT) Hepatic enzyme decreased (PT) Hepatic enzyme increased (PT)

Study Code: CSOM230B2410

Category	Adverse Event Term
	Hepatic function abnormal (PT) Hepatobiliary scan abnormal (PT) Hyperammonaemia (PT) Hypertransaminasaemia (PT) Liver function test increased (PT) Transaminases abnormal (PT) Transaminases increased (PT) Ultrasound liver abnormal (PT) Urine bilirubin increased (PT)
AESI Low blood cell related AEs	Anaemia (PT) Febrile neutropenia (PT) Haematocrit decreased (PT) Haemoglobin decreased (PT) Leukopenia (PT) Lymphocyte count decreased (PT) Lymphopenia (PT) Neutropenia (PT) Platelet count decreased (PT) Red blood cell count decreased (PT) Thrombocytopenia (PT)

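### No planned output counts concurrent ALT >3xULN with bilirubin >2xULN, or says how many patients had both tests done together

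*Protocol*

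**What the plan says.** Protocol 3.5.2.8 says that concurrent ALT >3xULN and bilirubin >2xULN has been seen in rare cases. It lists three situations in which therapy should stop: jaundice or other signs of clinically significant liver dysfunction; a transaminase rise ("in case of a sustained increase in AST or ALT of 5x ULN or greater"); and the combined criterion ("if ALT elevations greater than 3xULN occur concurrently with bilirubin elevations greater than 2xULN"). Neither document defines how close in time two results must be to count as concurrent.

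For analysis, Protocol 6.5.2.2 states: "The frequency of laboratory abnormalities will be summarized for each parameter". It adds shift tables and a listing: "A listing of laboratory values will be provided by laboratory parameter, patient and visit window". SAP 8.4.2 produces its summaries by laboratory parameter and direction of abnormality. The main table type is "Shift tables using CTC grades to compare baseline to the worst post-baseline value". SAP 8.4.2 also lists patients with values outside the reference range, and separately the laboratory values of patients with grade 3 or 4 abnormalities. The interim tables in SAP 2.2.1 include the same baseline-to-worst shift tables. Missing values are counted for each variable (Protocol section 6, SAP 4.1).

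In the suggested schedule (Protocol Table 3-1), the liver function row contains ALT, AST and alkaline phosphatase. Total bilirubin sits in the blood chemistry panel, which is suggested less often.

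**The concern.** Long-term safety is the primary objective, and Protocol 3.5.2.3 names increased liver enzymes as an important identified risk. The combined criterion is the more specific warning, and it depends on two results occurring together. A table of worst ALT and a separate table of worst bilirubin lose that link, because the two worst values in one patient may be months apart.

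The denominator is the second gap. Data are collected as available, and missing values are counted one variable at a time. If the report shows no case, a reader cannot tell from the tables whether patients with paired tests were free of the event or whether the two tests were seldom done together.

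**Working it through.** The documents give no rate, power figure or sample-size derivation for this event, so there is no plan figure to reproduce. The check has four steps.

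**1. Do any planned tables pair the two tests?**
- Protocol 6.5.2.2: frequency of abnormalities per parameter, and shift tables. No pairing.
- SAP 8.4.2: shift tables per parameter and direction, with extra categories only for HbA1c and fasting glucose. No pairing.
- SAP 2.2.1 (interim): baseline-to-worst shift tables. No pairing.
- SAP 8.4.1: adverse event tables by system organ class, preferred term or special-interest category. These count reported events, not laboratory values.
- Protocol 6.5.2.2 and SAP 8.4.2 listings: individual values, from which cases can be found by hand. They give no count or rate.

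**2. How often does the suggested schedule pair them?** Inputs are Table 3-1 and its footnotes, post-baseline, over 36 months, leaving out the end-of-treatment and end-of-study visits.
- ALT: weeks 1, 2, 4, 8 and 12 (5 times; week 12 taken as month 3), then every 3 months from month 6 to month 36 (11 times). Total 5 + 11 = 16.
- Total bilirubin: months 6, 12, 18, 24, 30 and 36. Total 6.
- Times with both: 6 of 16. In the first 12 weeks: 0 of 5.

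The schedule is only a suggestion, and a site may run bilirubin with every liver panel. Actual pairing could be higher or lower.

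**3. What do separate counts say about the joint count?** With *a* patients above the ALT limit and *b* above the bilirubin limit among *n*, the joint count lies between max(0, a + b − n) and min(a, b). Take a = 8 and b = 4 as assumed counts:
- n = 100: max(0, −88) = 0, min(8, 4) = 4, so 0 to 4 cases. As exact (Clopper-Pearson) 95% intervals, 0/100 is 0% (0 to 3.6%) and 4/100 is 4% (1.1 to 9.9%).
- n = 200: again 0 to 4 cases. 0/200 is 0% (0 to 1.8%) and 4/200 is 2% (0.5 to 5.0%).

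This range describes what the tables alone leave open. The listings would resolve it by hand.

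**4. What does a zero count mean for different denominators?** The exact two-sided 95% upper limit for 0 of *n* is 1 − 0.025^(1/n).

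| Patients with at least one pair | Upper limit |
|---|---|
| 200 (planned maximum, all paired) | 1.8% |
| 100 (planned minimum, all paired; or half of 200) | 3.6% |
| 50 (half of 100, assumed) | 7.1% |

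Halving the number of paired patients roughly doubles the rate that zero cases leave open.

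**The case against.** The strongest reply is that nothing is hidden. Any patient with recorded ALT >3xULN and bilirubin >2xULN is outside the reference range on both tests, so the SAP 8.4.2 out-of-range listing would contain that patient, provided the normal ranges are recorded. With 100 to 200 patients and an event described as rare, reading that listing is a small task. A patient who stopped for this reason may also appear among the adverse events leading to discontinuation. This stands as far as finding cases goes. It does not supply a count under a stated definition or a paired denominator. A patient who met the criterion and continued treatment would not be in the discontinuation tables.

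It is also fair to say that a new table would not narrow the limits in step 4, which depend on the number of patients. The table would show which limit applies.

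Four stronger readings are tempting, and the documents do not support them:
- **A trial stopping rule goes unmonitored.** Protocol 3.5.2.8 says therapy should be discontinued, and Protocol 3.2 and 3.5 state that the study imposes no therapy protocol. This is care guidance.
- **A promised analysis is missing.** No primary or secondary endpoint names the combined criterion.
- **The SAP is inconsistent because it tabulates QTc >480 ms.** The protocol requires those values to be reported as adverse events. No such rule covers the liver pair.
- **The adverse event outputs conceal the signal.** SAP 9.2 places ALT and blood bilirubin terms in different categories, and the exposure-adjusted tables show only preferred terms with more than 2 occurrences. Both concern reported terms and neither is designed to measure laboratory concurrence. The ordinary adverse event summaries carry no such cut.

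**Conclusion.** The gap is real and limited. As written, the plan yields no joint count, no rate and no number of patients with both tests done together for a signal that the protocol itself describes. Cases can still be found by hand from the listings.

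The size of the effect cannot be stated from the documents, because neither the event rate nor the extent of pairing is given. The counts of 8 and 4 and the halved denominators are illustrations. The 6-of-16 figure assumes Table 3-1 is followed literally. What holds without those assumptions is that separate worst-value tables cannot show concurrence, and that a report of no cases is hard to interpret without the paired denominator. Because the criterion is guidance and the study is descriptive, the priority is optional to modest.

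**What to change.** In SAP 8.4.2 add one on-treatment table (Day 1 to 28 days after last dose), overall and by cohort:
- Number and percentage of patients with ALT >3xULN and total bilirubin >2xULN within one stated window, for example the same day, with an exact 95% interval.
- Denominator: patients with at least one ALT-bilirubin pair in that window.
- Number with ALT >3xULN but no paired bilirubin.
- Number with a missing ULN for either test, since the ranges come from local laboratories.
- A short listing of the cases.

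Rows for AST, for sustained elevation at 5xULN, or for a 3-day window are optional extras.

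The cost is one table, one listing and a written definition of concurrence, programmed from values, dates and normal ranges that the study already plans to collect. No test, visit or data item is added. If the database is already locked, the table can go in the report labelled as post hoc.
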